6.1 Primary Endpoint

Effectiveness between treatment groups (FRIENDS and CATS) will be tested by calculating the 95% confidence limits (the width of the limit =|4.20|) for the differences in symptom severity, impairment, and academic competence (child outcomes) from pre to post between children receiving FRIENDS and children receiving CATS. If the calculated differences are within the 95% limit, then we will conclude that the two interventions have an equal impact or effect on child outcomes. If any of the differences in child outcomes is/are larger than the upper limit, then we will conclude that one intervention is better than the other. The limit of |4.20| was chosen based on the distribution of the reported mean effect sizes associate with FRIENDS.

Qualitative interviews with supervisors and therapists (perceived acceptability of support strategies) will be audio-recorded, transcribed and entered into NVivo 10.0 for coding and analysis. For each interview, a codebook (of common themes related to the appropriateness and acceptability of the support they received) will be developed and trialed by three coders based on an initial reading of the transcripts, and revised through discussions and subsequent transcript reviews. Coders will meet regularly to compare coding and revise the codebook. This will yield a stable set of qualitative codes that will be used to code the transcripts. Two independent coders will then code all of the transcripts. This iterative process will be continued until consensus is reached and saturation occurs. Coder reliability will be checked quarterly using the inter-rater reliability function in NVivo.

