6.3 Sample Size and Power

Number of students and statistical power. It is anticipated that a total of 284 (142 students per treatment protocol) will complete the proposed study. The published reported effect size of FRIENDS has been estimated to equal 0.56 (cohen's *d*). In testing for equivalence of FRIENDS and CATS, using two one-sided tests with sample sizes of 142 in FRIENDS and 142 in CATS achieves 88% power at a 5% significance level when the true difference between the means is 0 (null hypothesis), the standard deviation of the differences in means is assumed to be 11, and the equivalence limits are -4.20 and 4.20.

Number of therapist and statistical power. To compare TT to TT+ for the implementation of CATS (H2a), with 30 therapists in TT and 30 in TT+ achieve 86% power to detect a

difference of 8% between the null hypothesis that both group means are 80% (content fidelity) and the alternative hypothesis that the mean of group TT is 80% with estimated group standard deviations of 10 and 10 (an estimated effect size=.8) and with a significance level (alpha) of 0.05 using a two-sided two-sample t-test. Similarly, group sample sizes of 30 and 30 achieve 84% power to detect a difference of 0.7 in process fidelity between the null hypothesis that both group means are 4 and the alternative hypothesis that the mean of group TT+ is 4.7 with estimated groups standard deviations of 0.9 and 0.9 (an estimated ES= .78) and with a significance level (alpha) of 0.05 using a two-sided two-sample t-test.

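### The ±4.20 limit is about two thirds of the published FRIENDS effect at the plan's SD, so an unqualified verdict of equality claims more than meeting it would show

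*Combined protocol and SAP*

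**What the plan says.** Section 6.1 sets the decision rule for FRIENDS against CATS. If the pre-to-post differences lie within the limit, "then we will conclude that the two interventions have an equal impact or effect on child outcomes". The outcomes covered are symptom severity, impairment and academic competence, all with the same 4.20. The basis given for that number is: "The limit of |4.20| was chosen based on the distribution of the reported mean effect sizes associate with FRIENDS". No derivation follows. No scale is named, and nothing says how much of the FRIENDS effect CATS must keep.

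Section 6.3 supplies the other figures. "The published reported effect size of FRIENDS has been estimated to equal 0.56" (Cohen's d). The trial is sized "using two one-sided tests with sample sizes of 142 in FRIENDS and 142 in CATS", which "achieves 88% power at a 5% significance level" at a true difference of zero, where "the standard deviation of the differences in means is assumed to be 11" and "the equivalence limits are -4.20 and 4.20".

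**The concern.** CATS shortens FRIENDS from 12 sessions to 8 (section 1.2.1), and section 1.4 itself warns that adapting a treatment can make it less effective. The loss the comparison should guard against is thus a loss of benefit. When the limit is set beside the effect size quoted in section 6.3, it turns out to be a large part of that effect. A result inside the limit would still be reported as equality, with no statement of how wide the limit is. The effectiveness results also feed the cost-effectiveness analysis for agency administrators (section 6.2), so an unqualified verdict could be carried into adoption decisions without the limit attached.

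**Working it through.** **Inputs.** From section 6.3: limits ±4.20, SD 11, 142 per arm, 5% significance, true difference 0, stated power 88%, published d = 0.56.

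**1. Reproduce the plan's power.**
- SE = 11 × √(2/142) = 1.305.
- Power = 2 × Φ(4.20/1.305 − 1.645) − 1 = 88.4% by the normal approximation; 88.2% with the exact t calculation.
- At 2.5% per side (a 95% interval inside the limits) the exact figure is 78.7%, which does not match.
- The stated 88% thus stands, with 5% per side (a 90% interval) and 11 used as the SD of individual students. The 95% limits in section 6.1 do not correspond to this calculation.

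**2. The limit in SD units and against the published effect.**
- 4.20/11 = 0.38 SD, against 0.56 SD.
- Published effect in points, if its SD is 11: 0.56 × 11 = 6.16.
- 4.20/6.16 = 68%.

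**3. Dependence on the SD behind d.** The documents do not give this SD. For assumed values, the share is 4.20/(0.56 × SD):

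| Assumed SD behind d = 0.56 | Effect in points | Limit as share of effect |
|---|---|---|
| 7.5 | 4.20 | 100% |
| 9 | 5.04 | 83% |
| 11 | 6.16 | 68% |
| 13 | 7.28 | 58% |
| 15 | 8.40 | 50% |

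**4. How often a real loss would pass the section 6.3 tests.**
- With 142 per arm and SD 11, passing requires an observed difference below about 2.05 points in either direction, which is 2.05/6.16 = 33% of the effect.
- True loss of 3.08 points (half of 6.16): passes about 22% of the time (21.5%).
- True loss of 4.20 points: passes about 5%.

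**5. The same losses if only the point difference is compared with ±4.20.** The text of section 6.1 can be read this way.
- True loss of 3.08 points: Φ((4.20 − 3.08)/1.305) = 80%.
- True loss of 4.20 points: 50%.

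All these figures ignore clustering by school and treatment group, as the plan's own calculation does.

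**The case against.** The strongest objection is that the 68% joins two numbers the plan never joins. Section 6.3 does not say which outcome, comparator or SD lies behind d = 0.56, or that it shares a scale with the SD of 11. The limit is said to come from published effect sizes that cannot be inspected here, and the sponsor may hold a sound derivation. This stands, so the share is given conditionally and with its range.

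A second objection is that a margin is not an expected loss. This also stands. A reader might infer that CATS could lose most of the benefit and probably still be declared equal. The section 6.3 tests do not support that: a loss at the limit passes about one time in twenty. The chances rise to 50–80% only if section 6.1 is read as a rule on the point difference, and section 6.3 sizes the trial for a different procedure.

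A reader might also infer that passing guarantees CATS keeps at least 32% of the FRIENDS effect. That figure (100% − 68%) holds only at an SD of 11. Over the range in the table it runs from 0% to 50%, and it further assumes that the published effect applies in these schools. Nor can one percentage serve every instrument in section 5.2, since they are scored differently. Finally, a reader might want a tighter limit, such as half the effect. Nothing in the documents supports a particular retained share.

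Section 6.2 does give administrators intervals and acceptability curves as well as the verdict. That softens the consequence but leaves the section 6.1 conclusion unqualified.

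**Conclusion.** The concern holds as a mismatch between the limit and the words of the conclusion. The limit is 0.38 SD at the plan's SD, against a published effect of 0.56 SD. It is about 68% of that effect if the two SDs are comparable, and at least half for any SD behind d of up to 15. Passing the tests would show that the programmes differ by less than 4.20 points, not that they have equal effects. The sample size calculation is correct on its own terms, and no case is made that the limit itself must change. The pass rates of 5% and 22% rest on SD 11, 142 per arm, 5% per side and no clustering.

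**What to change.** Keep ±4.20 and the sample size. In section 6.1:

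- Replace the verdict of equality with: *equivalent within ±4.20 points (0.38 SD at SD 11, compared with a published FRIENDS effect of 0.56 SD)*.
- Allow that verdict only when the whole confidence interval used by the section 6.3 tests (90%, 5% per side) lies inside the limits, so that sections 6.1 and 6.3 describe one rule.
- Name the scale to which 4.20 and SD 11 apply, and restrict the verdict to it.
- Report the interval in SD units beside 0.56. Label any percentage of effect retained as resting on the assumption that the published effect has an SD comparable with 11.

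The sponsor should also show how 4.20 was derived. The cost is wording and one line of reporting, with no more children needed. The downside is a less favourable stated conclusion. The change should be made before results are known.

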3.2 Study Duration, Enrollment and Number of Sites

3.2.1 Duration of Study Participation

Agency Supervisors: There is no time limit placed on the duration of participation for agency supervisors. They may continue working with the research team for the duration of the study (5 years) or as long as their agency remains involved in the study or as long as they remain employed by the participating agency.

Agency (STS) Therapists Implementing EBP Interventions: Therapists are asked to commit to participate in the study for one school year. After the initial year, the study team would prefer to train a new therapist in an effort to minimize the effects of differences in therapist experience and therapist dropout on outcomes (yearly therapist dropout in the agencies is 25%). However, based on agency need and staff consideration, therapists can participate in additional years at the study team's discretion. This will be determined on a case-by-case situation. Therapists will be free to continue to implement the intervention groups outside the research project after participation in the study has concluded.

Students: Students who are determined to be eligible, based on the SCARED, and for whom consent/assent is obtained, will participate in a 30 minute baseline data collection session and then in the intervention which will consist of 12 (FRIENDS) or 8 (CATS) 40 minute (or one-class period) intervention sessions, conducted at school. They will also participate in a similar post-treatment data collection session once the intervention (12 or 8 sessions) is completed. Parents of the students participating in the intervention will also participate in two 30-minute data collection sessions (completion of the CBCL, CDI, and MASC-2, see section 5.2 below).

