3.2.2 Total Number of Study Sites/Total Number of Subjects Projected

The study will be conducted in a minimum of 36 (potentially up to 41) public K-8 schools within the School District of Philadelphia and in collaboration with community mental health agencies, contracted by CBH, in the City of Philadelphia. However, not every school will participate during every project year. It is anticipated that schools will participate in 2 project years.

We expect there to be a minimum of 36-41 agency supervisors (one per school at all times). However, there is a 17% drop-out rate of supervisors across agencies. Therefore, depending on supervisor turnover, the number of enrolled supervisors will be comparable. If

all therapists participate once per school year, we'd expect to enroll 90 agency therapists (1 therapist per school (n=18), per year of the study (n=5) = 18x5 = 90). However, given that therapists may run a second intervention group, we could end up with fewer therapists than expected. Yearly therapist drop out in the agencies is 25%. Therefore, depending on therapist turnover within the agencies, the number of enrolled therapists will also be comparable.

Each of the participating mental health agencies will make available extra supervisors and therapists to serve as alternates in case a supervisor or therapist drops out of the study or terminates employment with the agency for any reason. Alternate supervisors and therapists will be invited to attend the initial trainings. If a supervisor/therapist moves to another school within the same study arm, s/he will be allowed to remain in the study and will be treated as a returning supervisor. Supervisors/therapists in conditions A and B who move to a school assigned to a different study arm can participate in the project pending PI review. Supervisors/therapist in condition C who move to a new school assigned to condition A or B will not be allowed to continue in the study due to potential condition contamination. They will be counted as drop outs.

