The supervisions/consultation sessions will also be coded for interruptions and session length. Service interruption is defined as the degree to which therapists are fully available for supervision and treatment sessions. We will derive three scores averaged over the total number of sessions: a) Projected length of the session in minutes minus time spent on interruptions (e.g., answering a phone call, talking about unrelated topics); b) Number of interruptions; c) Total number of supervision / consultation and treatment sessions per group.

To measure differences between support strategies (TT vs. TT+), agency supervisors (12) and therapists (60) in all groups, including participants who did not complete a treatment group but were consented and trained to participate, will be interviewed regarding their perception of the appropriateness and acceptability of the support they receive. A study staff member will conduct open-ended, semi-structured interviews about the process, feasibility and acceptability of the type of support they receive. Interviewers will follow a script to ask questions of supervisors and therapists (e.g., "How acceptable is the level of support you received for the implementation of the FRIENDS protocol?"; "Was the supervision you received from your agency's supervisor appropriate for running groups with children?"; "Was the consultation you received from the research team appropriate for preparing you to conduct supervision with STS therapists?") These interviews will be conducted at the end of each academic year, or once the treatment groups have completed. Qualitative methods will be used because there are currently no psychometrically validated measures that address these areas.

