Kappa coefficients will be computed; a minimum of .85 will be required for each code. Retraining will be conducted should rater agreement fall below .85. In order to aid with interpretation of results, IE's will randomly select an additional 35% of the interviews and code them, as a measure of inter-rater-reliability. We will conduct a structured content analysis for perceived acceptability and appropriateness. The unit of analysis is each interview. We will create a case-by-variable matrix from the codes. The matrix will have an interviewee identifier number, type of support (i.e., TT, TT+), school, agency, subject demographic information, and codes. The code cells will contain the number of times the participant emitted words or phrases pertaining to perceived acceptability and appropriateness of the support they received. Once acceptability and appropriateness are defined for each interview, percentages for acceptability (% acceptance) and appropriateness (% appropriate) out of the total number of words will be calculated. Comparison of % acceptance and % appropriate between TT, TT+ will be conducted using the Wilcoxon sum rank test.

Datasets from the REDCap and NVivo databases will be combined using the statistical software SAS. Each session will be considered to be a "case" in the qualitative database and will be assigned a unique identifying number that will link it (anonymously) to the quantitative database and individual session information such as fidelity scores.

To measure the differences of implementation between therapists whose supervisors receive TT vs. TT+, means of content fidelity will be calculated with its 95% Confidence interval. Similar analysis will be done regarding process fidelity.

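### The TT versus TT+ interview comparison takes each interview as the unit, so repeat interviews of the same supervisor would push its false-positive rate above 5%, by an amount that depends on repeats per supervisor

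*Combined protocol and SAP*

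**What the plan says.** All references are to the combined protocol and SAP.

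- **Unit and test (6.1).** "The unit of analysis is each interview". Then: "Comparison of % acceptance and % appropriate between TT, TT+ will be conducted using the Wilcoxon sum rank test".
- **Data layout (6.1).** "The matrix will have an interviewee identifier number, type of support (i.e., TT, TT+), school, agency, subject demographic information, and codes". A person identifier is therefore recorded, but the named test does not use it.
- **Timing (5.3).** "These interviews will be conducted at the end of each academic year, or once the treatment groups have completed".
- **Who is interviewed (5.3).** "agency supervisors (12) and therapists (60) in all groups". Section 3.2.2 instead expects at least 36-41 supervisors, one per school.
- **Supervisor repeats (3.2.1, 8.1.1).** "There is no time limit placed on the duration of participation for agency supervisors"; they may stay for all 5 years. Section 8.1.1 foresees the same supervisors coming back. It aims to hold them in one support condition, TT (A or B) or TT+ (C), across the first two randomization lists. The third list, for year 5, is not mentioned there.
- **Therapist repeats.** Section 8.1.1 has each therapist taking part once. Section 3.2.1 allows further years case by case.
- **Changes of arm (3.2.2).** Staff in A or B may move to another arm, subject to review by the principal investigator when they change school. Staff in C may not leave C and stay in the study.

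No section says how several interviews from one person are to be combined.

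**The concern.** The rank-sum test needs independent observations. Two interviews of one supervisor, a year apart and under the same support type, are likely to resemble each other. Entered as separate rows in the same group, they make the test statistic more variable than its reference distribution allows, so a true null is rejected too often. Such a supervisor also weighs more: five interviews count five times as much as those of a therapist interviewed once.

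At stake is the only between-arm test named for acceptability and appropriateness of support. Section 5.3 says there is no validated measure to fall back on. A school or therapy-group term in the child or fidelity analyses would not help, because the problem lies in this test's own unit of analysis.

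**Working it through.** **1. The plan's own figures.** The plan gives no alpha, power or sample size for this test, so there is nothing of its own to reproduce. The nearest figures are the TT versus TT+ fidelity powers in section 6.3 (30 per group, two-sided t-test, alpha 0.05). The noncentrality is difference/(SD × √(2/30)):
- content fidelity: 8/(10 × 0.258) = 3.10, power 86.1% (stated 86%);
- process fidelity: 0.7/(0.9 × 0.258) = 3.01, power 84.2% (stated 84%).

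Both reproduce. The two-sided 5% level is borrowed from them.

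**2. How many repeats the schedule implies.** Section 8.1.1 has 6 schools per arm per year for 5 years. With one supervisor per school this is 6 × 5 = 30 supervisor-years per arm, or 90 over three arms.
- If the 12 supervisors of section 5.3 are the people covering B and C: 60/12 = 5 years each on average.
- With 36-41 supervisors over all arms: 90/36 = 2.5 down to 90/41 = 2.2 years each. Section 3.2.2 also expects schools to take part in 2 years.

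Either count gives more than one year per supervisor.

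**3. Error rate.** Let *s* be supervisors and *t* therapists per arm, *m* interviews per supervisor and ρ the within-supervisor correlation. Therapists are interviewed once. *m* and ρ are assumptions. Then

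Deff = [t + s·m·(1 + (m − 1)ρ)] / (t + s·m), actual α = 2·[1 − Φ(1.96/√Deff)].

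Examples at ρ = 0.5:
- s = 6, t = 30, m = 2: Deff = (30 + 12 × 1.5)/42 = 1.14, α = 6.7%.
- s = 12, t = 30, m = 3: Deff = (30 + 36 × 2)/66 = 1.55, α = 11.5%.
- s = 6, t = 30, m = 5: Deff = (30 + 30 × 3)/60 = 2.00, α = 16.6%.

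Simulation of the rank-sum test under no difference (20,000 replicates per cell), in %:

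| Supervisors + therapists | m | ρ = 0.3 | ρ = 0.5 | ρ = 0.7 |
|---|---|---|---|---|
| 6 + 30 per arm | 2 | 6.1 | 6.4 | 7.1 |
| 6 + 30 per arm | 3 | 7.7 | 9.0 | 11.1 |
| 6 + 30 per arm | 5 | 12.1 | 15.6 | 20.6 |
| 12 + 30 per arm | 2 | 6.6 | 7.4 | 8.4 |
| 12 + 30 per arm | 3 | 9.1 | 11.6 | 13.4 |
| TT = A and B: 8 + 40 v 4 + 20 | 2 | 5.7 | 6.5 | 6.8 |
| TT = A and B: 8 + 40 v 4 + 20 | 5 | 11.9 | 16.8 | 20.4 |
| Supervisors only, 6 v 6 | 2 | 7.9 | 10.5 | 13.3 |
| Supervisors only, 6 v 6 | 5 | 18.0 | 25.6 | 32.2 |

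With one interview each, 6 + 30 per arm gives 4.8%. The row with 12 supervisors and m = 3 uses 12 × 3 = 36 supervisor-years per arm, slightly more than the 30 scheduled, so it is towards the upper end for that count.

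**4. After the change.** With one averaged value per person at ρ = 0.5 and m = 2 or 5, the simulated rate is 4.7-4.9% (6 + 30 per arm), 4.8-5.0% (12 + 30 per arm) and 4.1-4.3% (supervisors only, 6 v 6). These runs treat different people as independent.

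**The case against.** The best defence is that re-interview is inferred. Section 5.3 gives a headcount, and its timing could mean that each yearly cohort is interviewed once, when it finishes. A matrix keyed by interviewee fits one row per person. The unit-of-analysis sentence may only mean interview rather than word or code. This reading is possible, but no section says so. With returning supervisors and year-end interviews, the sentence as written yields repeat rows.

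A reader might infer that the false-positive rate is well above 5%. The documents do not support that. They give neither interviews per supervisor nor a correlation. At the 2 years expected per school the excess is small, and the high figures need every supervisor interviewed in all 5 years. Support type is held only for the first two lists. Anyone moving from A or B into C puts correlated interviews on opposite sides, which offsets part of the inflation and was not modelled.

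A reader might also infer that returning therapists add much to the problem. Section 8.1.1 says that each takes part once, so this rests on the exception in 3.2.1.

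The importance is limited too. The test sits under the primary endpoint heading, but the TT versus TT+ outcomes with stated power are content and process fidelity.

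**Conclusion.** The point stands in a conditional form. If repeat supervisors are interviewed each year, the stated unit and test treat their interviews as independent and the false-positive rate exceeds a nominal two-sided 5%. With therapists interviewed once and an assumed within-person correlation of 0.3-0.7, the rate is:

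- about 6-9% at two interviews per supervisor;
- about 9-13% at three, with 12 supervisors per arm;
- about 12-21% only if 6 supervisors per arm are all interviewed in all 5 years.

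A supervisors-only comparison would fare worse, but the plan does not specify one. Since the plan sets a definite rule and already records the identifier needed to correct it, this is more than a missing detail.

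**What to change.** In section 6.1:

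1. Make the person the unit of analysis. Average each interviewee's percentage acceptance and percentage appropriateness over that person's interviews, and apply the rank-sum test to one value per person. Keep the yearly interviews for description.
2. For anyone interviewed under both support types, use only the interviews under the first assigned type.
3. State that averaging removes the repeat-interview dependence only. Schools are randomized and therapists can share a supervisor, so correlation within supervisor and school remains. A rank test clustered by supervisor or school would address that as well.

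Using only the first interview, or permuting support type by person, would be a different analysis, not an equivalent one.

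Reconcile the supervisor counts (12 in 5.3, 36-41 in 3.2.2) and the statements on therapist repeats (3.2.1, 8.1.1). If one interview per person was always intended, saying so settles the main point.

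The cost is a short edit and one data step, with no new data. The downside is a smaller nominal sample size.

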If substantial time (45-90 days) has lapsed between training and the start of intervention, Supervisors will be offered a booster training session after the original training in the weeks before starting their group. The purpose of the booster session is to review key points from the training (e.g., conducting performance feedback) and to answer questions about any aspect of the supervision process. This subsequent training opportunity for agency

supervisors (on how to be effective supervisors to the implementing therapists) will be conducted remotely, or in person.

Supervisors in TT+ (Group C) will receive 8 consultation sessions in the first year using the online platform. The consultation sessions will center on helping the supervisor conduct supervision, and will include performance feedback, implementation fidelity, problem solve implementation barriers and will answer supervisors' questions about the supervision manual. We will monitor whether supervision with therapists takes place regularly for the expected length of time and whether therapists implement the treatments with fidelity. This information will be obtained from group fidelity scores.

Supervisors will be instructed to supervise therapists based only on what they have learned in the consultation sessions.

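### The % acceptance and % appropriate scores count mentions of the topic per word spoken, so a TT versus TT+ difference in them cannot be read as a difference in acceptability

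*Combined protocol and SAP*

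**What the plan says.** Section 5.3 plans semi-structured interviews with 12 supervisors and 60 therapists on how acceptable and appropriate they found the support. It gives the lack of validated instruments in this area as the reason for using qualitative methods.

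Section 6.1 sets out the scoring in four steps.

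- Codebook: "a codebook (of common themes related to the appropriateness and acceptability of the support they received) will be developed" from an initial reading of the transcripts. Two independent coders then code every transcript, with kappa of at least .85 required for each code.
- Counts: "The code cells will contain the number of times the participant emitted words or phrases pertaining to perceived acceptability and appropriateness of the support".
- Percentages: "Once acceptability and appropriateness are defined for each interview", the plan says, "percentages for acceptability (% acceptance) and appropriateness (% appropriate) out of the total number of words will be calculated".
- Test: "Comparison of % acceptance and % appropriate between TT, TT+ will be conducted using the Wilcoxon sum rank test".

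On the extra support in TT+, section 3.1.3 says: "Supervisors in TT+ (Group C) will receive 8 consultation sessions in the first year using the online platform". Section 8.8 provides payment for consultation time only to Condition C supervisors. One of the sample interview questions in section 5.3 is: "Was the consultation you received from the research team appropriate for preparing you to conduct supervision with STS therapists".

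**The concern.** A mention can pertain to acceptability whether it praises or criticises. An interviewee who says repeatedly that the supervision was not acceptable adds to the count just as one who praises it does. The result is nevertheless labelled % acceptance.

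The denominator is a second problem. It is every word in the interview, including talk that has nothing to do with the support. The proportion therefore says how much of the conversation touched the topic, not what share of the expressed opinion was positive.

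Comparing TT with TT+ is one of the primary objectives in section 2.1, and this analysis appears under the primary endpoint. The documents plan no other measure of acceptability that could act as a check. If the score does not track opinion, a significant Wilcoxon result could favour the strategy that staff liked less, and a null result could hide a real difference in opinion.

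**Working it through.** The plan gives no target value, sample size, power or significance level for the interview scores, so there is no figure to reproduce. The check applies the scoring rule as written. All word and mention counts below are assumptions, because the documents give none.

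**Notation.** F is the number of favourable mentions in an interview, U the number of unfavourable mentions and W the total words.

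- Score as written (section 6.1): (F + U) / W
- Score with direction: F / (F + U)

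**Step 1: direction.** In the written score F and U are interchangeable, so at equal length the ranking depends only on the total number of mentions.

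| Assumed interview | F | U | W | As written | With direction |
|---|---|---|---|---|---|
| Dissatisfied | 0 | 20 | 3,000 | 20/3,000 = 0.67% | 0/20 = 0% |
| Satisfied | 5 | 0 | 3,000 | 5/3,000 = 0.17% | 5/5 = 100% |
| Dissatisfied | 2 | 28 | 2,000 | 30/2,000 = 1.5% | 2/30 = 6.7% |
| Satisfied | 20 | 0 | 2,000 | 20/2,000 = 1.0% | 20/20 = 100% |

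Both pairs are ranked the wrong way round as written. In the first pair the ratio is 20/5 = 4 at any common length: 1.33% against 0.33% at 1,500 words, and 0.33% against 0.08% at 6,000. The reversal is possible rather than inevitable. It occurs whenever the dissatisfied person raises the topic more often per word.

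**Step 2: denominator.** Suppose only favourable mentions were counted, still over all words. In 3,000 words, an interviewee with 5 favourable and no unfavourable mentions scores 5/3,000 = 0.17%. One with 10 favourable and 10 unfavourable scores 10/3,000 = 0.33%. The evenly divided interviewee scores twice the wholly positive one; with direction the figures are 50% and 100%. Counting favourable mentions alone therefore does not repair the score.

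Uncoded talk matters too. Twenty mentions in 3,000 words give 0.67%. Adding 3,000 words with no coded mention gives 20/6,000 = 0.33%, with no change of opinion.

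**Step 3: extra content in TT+.** Start from 20 mentions in 2,000 words (1.0%) and add 500 words about consultation, with a fraction r of coded mentions per word. The score becomes (20 + 500r) / 2,500.

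| r | Score |
|---|---|
| 0.5% | 22.5/2,500 = 0.9% |
| 1.0% | 25/2,500 = 1.0% |
| 1.5% | 27.5/2,500 = 1.1% |
| 2.0% | 30/2,500 = 1.2% |

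The added talk enters both numerator and denominator. The score rises only if that talk is denser in coded mentions than the rest of the interview; otherwise it stays the same or falls.

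**The case against.** The strongest reply is that the plan is silent on direction rather than wrong about it. The codebook has yet to be developed and may well separate praise from criticism. A defining step comes before the percentages are formed, and the labels suggest that favourable content is meant. This stands in part: nothing says that complaints are intended to count as acceptance, and a reader should not infer that. But neither opening supplies a rule for direction, and Step 2 shows that the total-words denominator would remain a fault even if one were added. A definition settled only after the transcripts are read would also make the score's meaning depend on the data. Kappa does not help here, since it shows that coders agree, not that the score measures acceptance.

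A second reply is that dividing by words is a sensible adjustment for length, since raw counts would reward talkativeness. That is fair as far as it goes: if coded content grows in proportion to length, the score is unchanged. The halving in Step 2 holds only when the added words are uncoded. Adjusting for length still does not turn frequency of mention into a rate of acceptance.

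A third reply is that little hangs on this test. No significance level, power or decision rule is attached to it, and the therapist sample size in section 6.3 rests on content and process fidelity. This stands, and it limits the consequence to the interpretation of the acceptability and appropriateness results.

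A reader might also infer that TT+ scores are inflated because that arm has more support to talk about. The documents do not support this. Step 3 shows that the direction is open. Consultation goes directly only to supervisors, who are 12 of the 12 + 60 = 72 interviewees planned in section 5.3 across all groups. The sample questions are examples only, and the plan does not say who is asked the one about consultation.

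**Conclusion.** The concern holds for the score itself. Followed as written, section 6.1 produces a frequency of mention per word, without direction, under a label that says acceptance. A TT versus TT+ difference on it, in either direction, cannot be read as a difference in acceptability or appropriateness. Differences in interview content between arms may add to the problem, but neither their size nor their sign can be fixed from the documents.

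The fourfold reversal illustrates what the rule allows; it does not predict what the interviews will show. It rests on assumed counts and on taking the stated rule literally. The conclusion needs only that favourable and unfavourable mentions enter the count alike, or that all words form the denominator. The fidelity comparisons and their power are not affected.

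**What to change.** Amend section 6.1 before coding starts.

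- Require each acceptability or appropriateness mention to be coded as favourable or unfavourable.
- Define % acceptance as favourable mentions divided by favourable plus unfavourable mentions in that interview, and % appropriate in the same way.
- State how interviews with no coded mentions are handled, since the ratio is then undefined. For example, report their number by arm and leave them out of the Wilcoxon test.

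A sensitivity comparison without the answers to the consultation question is optional. It should not replace the main comparison, because consultation is what distinguishes TT+ from TT and leaving it out would discard direct opinion on that component.

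The cost is one added attribute on transcripts that two coders already read in full, with no new data collection. That attribute must also reach kappa .85, which may mean some retraining. The ratio is unstable when mentions are few: with a single mention it can only be 0% or 100%, and with four mentions one change of code moves it by 25 percentage points. The number of mentions per interview should therefore be reported beside the score.
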